### **5.5.7 Concomitant medication**

The investigator must instruct the subject to notify the study site about any new medications they take after being enrolled into the study. All medications, procedures and significant non-drug therapies (including physical therapy and blood transfusions) administered after the subject was enrolled into the study must be recorded in the Concomitant Medications/Significant Non-Drug Therapies eCRF.

Each concomitant medication must be individually assessed against all exclusion criteria and prohibited medications. If in doubt the investigator should contact the Novartis medical monitor before randomizing a subject or allowing a new medication to be started.

### 5.5.8 Prohibited medication

Use of the treatments displayed in [Table 5-2](#) is not allowed after subjects have become eligible for participation into the study during the screening period. At the latest, subjects should stop using the medications listed in [Table 5-2](#) at the start of Epoch 2.

**Table 5-2 Prohibited medication**

Medication/product	Prohibition period	Action taken
St. John's wort (strong CYP3A inducer)	Entire study	Discontinue prohibited medication during the screening period once subject is eligible for participation in the study
GLP-1 agonists	Entire study	Discontinue prohibited medication during the screening period once subject is eligible for participation in the study
SGLT2 inhibitors other than study medication	Entire study	Discontinue prohibited medication during the screening period once subject is eligible for participation in the study
Pharmacologically active weight-loss medication	Entire study	Discontinue prohibited medication during the screening period once subject is eligible for participation in the study

Some medications or products must be used with caution:

- Use of grapefruit juice (strong inhibitor of CYP3A4) should be discouraged and its consumption must not happen within 2h of study medication intake.
- Use of antibiotic or antifungal medications that are strong inhibitors of CYP3A4 should be limited to 10 days during the study. Examples of such medications are clarithromycin, telithromycin, itraconazole, ketoconazole, voriconazole or posaconazole.
- Use of strong UGT inhibitors such as probenecid, valproic acid or mefenamic acid should be limited to 10 days during the study.

### 5.5.9 Emergency breaking of assigned treatment code

Emergency code breaks must only be undertaken when it is required in order to treat the subject safely. Most often, study treatment discontinuation (TD) and knowledge of the possible treatment assignments are sufficient to treat a study subject who presents with an emergency condition. Emergency treatment code breaks are performed using the IRT system. When the investigator contacts the system to break a treatment code for a subject, the requested subject identifying information must be provided and the necessity to break the treatment code must be confirmed. The investigator will then receive details of the investigational drug treatment for the specified subject and a communication confirming this information. The system will automatically inform the Novartis monitor for the site and the study team that the code has been broken.

It is the investigator's responsibility to ensure that there is a dependable procedure in place to allow access to the IRT system at any time in case of emergency. The investigator will provide the protocol number, the study drug name (if available) and the subject number.

In addition, oral and written information to the subject must be provided on how to contact the investigator's backup in case of emergency, or when the investigator is unavailable, to ensure that un-masking can be performed at any time.

Subjects whose treatment has been unmasked must be discontinued from the study treatment (see [Section 5.6.2](#)).

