### **5.6.2 Discontinuation of study treatment**

Discontinuation of study treatment for a subject occurs when study drug is stopped earlier than the protocol planned duration, and can be initiated by either the subject, the investigator or the sponsor (see [Section 5.6.5](#)).

The investigator must discontinue study treatment for a given subject if, on balance, she/he believes that continuation would negatively impact the risk/benefit of study participation.

Study treatment must be discontinued under the following circumstances:

- Subject wish.
- Pregnancy, see [Section 6.5.5](#) and [Section 7.6](#).
- Use of prohibited treatment, see [Section 5.5.8](#).
- Any situation in which study participation might result in a safety risk to the subject.
- Emergence of the following AE: ketoacidosis (see also [Section 7.8.1](#)) or lower limb amputation (including toe amputation).
- Any laboratory abnormalities that in the judgment of the investigator, taking into consideration the subject's overall status, prevents the subject from continuing participation in the study.
- Subjects whose study treatment has been unmasked (see [Section 5.5.9](#)).
- Withdrawal of consent (see [Section 5.6.3](#)).

If discontinuation of study treatment occurs, the subject should *not* be considered withdrawn from the study. The subject should return to the study site as soon as possible after

discontinuation of study drug for a study treatment discontinuation visit (see [Table 6-1](#)). TD visit assessments detailed in [Table 6-1](#) should be completed and recorded in the eCRF. The investigator must determine the primary reason for the subject's premature discontinuation of study treatment and record this information on the appropriate eCRF.

After study treatment discontinuation, at a minimum, in abbreviated visits, the following data should to be collected at study site visits or via telephone contact:

- New and/or concomitant treatments.
- AEs/Serious AEs (SAEs).

If the subject cannot or is unwilling to attend any visit(s), the site staff should maintain regular telephone contact with the subject, or with a person pre-designated by the subject. This telephone contact should preferably be done according to the study visit schedule ([Table 6-1](#)).

The investigator must also contact the IRT system to register the subject's discontinuation from study treatment. If study drug discontinuation occurs because treatment code has been broken, please refer to [Section 5.5.9](#).

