5.4 Rule of exclusion criteria of analysis sets

Protocol deviations are identified prior to clinical database lock/unblinding and entered into a dedicated data panel as part of the locked database. Details are provided in the PD Specs and Edit Checks tab of LIK066B2201 Edit Check Specification document.

The protocol deviations resulting in exclusion of subjects from an analysis population are outlined in Table 5-1 below.

Table 5-2 Protocol deviations that cause subjects to be excluded

Deviation ID	Description of Deviation	Exclusion in Analyses
INCL01	Informed consent not obtained	Excluded from SCR, RUN, RAN, FAS, SAF, and PPS
TRT19	Subject withdrew consent and not discontinued from the study	Data collected after withdrawal of IC, excluded from FAS and SAF
TRT34	Patients mis-randomized in IRT	Excluded from FAS and PPS
INCL03	BMI not within range or BMI missing	Excluded from PPS
EXCL04	Subject taking prohibited medication	Excluded from PPS
EXCL05	Patient with a history of malignancy	Excluded from PPS
EXCL06	Pregnant patient	Excluded from PPS
EXCL08	Use of active weight-loss medications	Excluded from PPS
EXCL09	Bariatric surgery	Excluded from PPS
EXCL10b	Not compliant with lifestyle intervention	Excluded from PPS
EXCL19	Substances or alcohol abuse	Excluded from PPS
TRT06	Study treatment adjusted	Excluded from PPS
TRT11	Study treatment unmasked and subject not discontinued from the study	Excluded from PPS
TRT15	Use of prohibited medication and not discontinued from the study	Excluded from PPS
TRT22	Use of another investigational drug while on study	Excluded from PPS
TRT35	Study medication taken after the morning or evening meal	Excluded from PPS
TRT28	Misdispensed medication and taken by patient	Excluded from PPS

[figure not shown]
Table 5-3 Subject Classification

Analysis Set	PD ID that cause subjects to be excluded	Non-PD criteria that cause subjects to be excluded
SCR	INCL01	Not having screening epoch disposition page

Analysis Set	PD ID that cause subjects to be excluded	Non-PD criteria that cause subjects to be excluded
RUN	INCL01	Not in ENR; Not having run-in epoch disposition page
RAN	INCL01	Not randomized
FAS	INCL01, TRT19, TRT34	Not in RAN;
PPS	INCL01, INCL03, EXCL04, EXCL05, EXCL06, EXCL08, EXCL09, EXCL10b, EXCL19, TRT06, TRT11, TRT15, TRT22, TRT35, TRT 28, and TRT34	Overall exposure on DB medication < 22 weeks unless premature discontinuation due to adverse events
SAF	INCL01, TRT19	No double-blind study drug taken

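### SAP deviations TRT11 and TRT15 depend on whether the subject left the study, while the protocol rule is about stopping study treatment, so in a few narrow cases per-protocol membership follows follow-up status rather than the violation

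*Protocol*

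**What the plan says.** **Protocol.** Section 5.5.9 says: "Subjects whose treatment has been unmasked must be discontinued from the study treatment". Section 5.6.2 lists both unmasking and use of prohibited treatment among the circumstances in which study treatment has to stop. It then says that after such a stop "the subject should *not* be considered withdrawn from the study".

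**SAP, deviations.** Table 5-2 (Section 5.4) describes TRT11 as "Study treatment unmasked and subject not discontinued from the study" and TRT15 as "Use of prohibited medication and not discontinued from the study". Both lead to exclusion from the PPS. Neither appears in the full analysis set (FAS) row of Table 5-3. The same table has EXCL04, "Subject taking prohibited medication", and EXCL08 for weight-loss medication. Their numbers match entry exclusion criteria 4 and 8, and the SAP does not say whether they also apply after randomisation.

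**SAP, exposure gate.** Section 2.2 requires at least 22 weeks of exposure for the PPS and states no exception. The PPS row of Table 5-3 excludes subjects with "Overall exposure on DB medication < 22 weeks unless premature discontinuation due to adverse events". Protocol 9.1 asks only for one dose and has no 22-week gate.

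**Use.** The PPS supports a sensitivity analysis of the dose-response model (protocol 9.4.4, SAP 2.5.4). The primary analysis uses the FAS (protocol 9.4.1, SAP 2.5.1).

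**The concern.** Stopping study drug and leaving the study are different events, and Section 5.6.2 of the protocol takes care to separate them. TRT11 and TRT15 are worded on the second event. A site that does what the protocol asks, stopping drug and keeping the subject in follow-up, therefore produces the status that the SAP counts as a deviation.

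Take two subjects who are unmasked because of an adverse event and stop drug at week 10. One stays in the study. TRT11 removes that subject from the PPS. The other leaves the study. TRT11 does not apply, the adverse-event exception in Table 5-3 keeps the subject in, and the missing Week 24 weight is imputed. Adherence and reason for stopping are the same. Only follow-up differs, and the subject with more follow-up is the one dropped.

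At stake is whether the per-protocol set selects on adherence, as a reader of the sensitivity analysis will assume. There is also a reproducibility problem: a programmer following the literal text and one following the protocol would build different sets.

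**Working it through.** The documents state no figure on this point, so there is nothing to reproduce. The check is a truth table for a subject who has been unmasked or has used prohibited medication after randomisation, with no other deviation.

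**Definitions**
- Stopped: study drug was stopped in response, as protocol 5.6.2 requires.
- Left: the subject left the study.
- As written: the deviation applies if the subject has not left the study (TRT11 and TRT15 read literally).
- Aligned: the deviation applies if study drug was not stopped.
- Gate A (SAP Table 5-3): exposure of at least 22 weeks, or a stop due to an adverse event (AE).
- Gate B (SAP 2.2): exposure of at least 22 weeks, no exception.
- In the PPS: passes the gate and the deviation does not apply.

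| Row | Stopped | Left | ≥22 wk | AE stop | A: as written | A: aligned | B: as written | B: aligned |
|---|---|---|---|---|---|---|---|---|
| 1 | yes | yes | yes | yes | in | in | in | in |
| 2 | yes | yes | yes | no | in | in | in | in |
| 3 | yes | yes | no | yes | in | in | out | out |
| 4 | yes | yes | no | no | out | out | out | out |
| 5 | yes | no | yes | yes | out | **in** | out | **in** |
| 6 | yes | no | yes | no | out | **in** | out | **in** |
| 7 | yes | no | no | yes | out | **in** | out | out |
| 8 | yes | no | no | no | out | out | out | out |
| 9 | no | yes | yes | – | in | **out** | in | **out** |
| 10 | no | yes | no | – | out | out | out | out |
| 11 | no | no | yes | – | out | out | out | out |
| 12 | no | no | no | – | out | out | out | out |

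**Result.** Under gate A, membership changes in 4 of 12 rows: three are out as written but in when aligned (5, 6, 7), and one is in as written but out when aligned (9). Under gate B it changes in 3 rows (5, 6 and 9). These are counts of logical cases, not of subjects.

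**How narrow rows 5 and 6 are.** The gate is 22 × 7 = 154 days of a 24 × 7 = 168-day epoch. Within Epoch 3 the wording matters for a stop without an adverse event only in the last 14 days, 14/168 = 8.3% of the epoch. That is a share of time. It is a share of stops only if stop times are assumed uniform.

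**Row 7** exists only under gate A. Protocol 5.5.9 restricts code breaks to cases where safe treatment requires them, so adverse-event stops among unmasked subjects are plausible, but the documents give no frequency.

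**TRT15 judged on use alone.** If any post-randomisation use of prohibited medication should exclude, every row is out. The literal text then wrongly keeps the leavers who pass the gate: rows 1, 2, 3 and 9 under gate A, and rows 1, 2 and 9 under gate B. Aligning TRT15 to drug stopping would leave rows 1 to 3 in (1 and 2 under gate B) and would add rows 5 to 7 (5 and 6 under gate B), so it is the wrong repair for that code.

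**Limit of the table.** An adverse-event stop is tabulated only for subjects who stopped under the rule. Someone who carried on and later left because of an adverse event before week 22 would behave like row 9 under gate A.

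**The case against.** **The 22-week gate does most of the work.** This stands. A subject who stops before week 22 without an adverse event is out under either wording (row 8), and the adverse-event case depends on an exception that SAP 2.2 does not contain. It limits the effect but does not remove it.

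**Ordinary violators are caught.** This stands too. A subject still on drug and still in the study is flagged as written (rows 11 and 12). A reader might infer that protocol-compliant subjects generally drop out of the PPS and violators generally stay in. The table does not support that.

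**TRT15 subjects took a prohibited drug, so excluding them is sensible, and EXCL04 may catch them anyway.** The first part stands and shapes the fix. The second is open: EXCL04 has no stated limit to entry, but its number is that of an entry criterion and the SAP does not settle it.

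**The phrase may be stock shorthand, and the programmed rule sits in an edit-check specification that is not available here.** That is possible. But TRT19 in the same table uses the phrase for consent withdrawal, where leaving the study is what is meant. The hypoglycaemia text in SAP 2.8.1.1 also separates stopping medication from withdrawing from the study. Shorthand is not established.

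**A reader might also infer that the wording pushes sites to withdraw subjects, costing the FAS Week 24 weights.** Nothing supports this. SAP 5.4 says only that deviations are identified before database lock, and protocol 5.6.2 tells sites that the subject is not withdrawn. Weight is also not among the minimum data that section asks for after a drug stop, so it may be missing in any case.

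**Conclusion.** The two documents conflict, and they need to be reconciled. Read literally, TRT11 and TRT15 make exclusion depend on follow-up status. The reach is small:

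- wrongly excluded, if the protocol's handling rule is the yardstick: subjects who stopped drug and stayed in, with an adverse-event stop (Table 5-3 gate only) or at least 22 weeks of exposure;
- not caught: a violator who continued to at least 22 weeks and then left the study, provided no other deviation code applies.

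The number of subjects affected cannot be computed. The documents give no rate of unmasking or prohibited use. Applying an assumed rate to the 432 planned subjects would count everyone unmasked or using such drugs, not those whose membership changes.

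Only the PPS sensitivity analysis is affected. TRT11 and TRT15 exclude nobody from the FAS, so the primary estimate, its type I error and its power do not change.

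The conclusion assumes that Table 5-2 is applied as worded and that EXCL04 and EXCL08 are confined to entry. If they also cover post-randomisation use, the TRT15 part largely falls away and the TRT11 part remains.

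**What to change.** In the SAP, before treatment codes are unblinded for the analysis concerned:

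1. Reword TRT11 so that it applies when treatment was unmasked and study treatment was not then discontinued.
2. Base TRT15 on post-randomisation use of prohibited medication itself, with no condition on study status. Alternatively, state that EXCL04 and EXCL08 apply after randomisation. Do not give TRT15 the TRT11 wording, because that could admit users of prohibited weight-loss drugs to the PPS.
3. Reconcile SAP 2.2 with Table 5-3 on the adverse-event exception to the 22-week gate.
4. Align the edit-check specification with the result.

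This concerns analysis-set definitions only and leaves the protocol's treatment rules as they are. The cost is a few lines of SAP text and the matching checks, with no new data.

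The SAP's document history has an entry of May 2018 that refers to Week 24 results. If the Week 24 PPS was already fixed by then, the report should state which rule was programmed, and any rerun under the revised rule should be labelled post hoc.

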## **5.6 Study completion and discontinuation**

### **5.6.1 Study completion and post-study treatment**

A subject will be considered to have completed the study when the subject has completed the last planned visit (see [Table 6-1](#)). The study as a whole will be considered completed when all randomized subjects have completed the last visit planned in the protocol (see [Table 6-1](#)) or have discontinued the study prematurely.

For subjects who are loss to follow-up, see [Section 5.6.4](#).

The investigator must provide follow-up medical care for all subjects who are prematurely withdrawn from the study, or must refer them for appropriate ongoing care.

### **5.6.2 Discontinuation of study treatment**

Discontinuation of study treatment for a subject occurs when study drug is stopped earlier than the protocol planned duration, and can be initiated by either the subject, the investigator or the sponsor (see [Section 5.6.5](#)).

The investigator must discontinue study treatment for a given subject if, on balance, she/he believes that continuation would negatively impact the risk/benefit of study participation.

Study treatment must be discontinued under the following circumstances:

- Subject wish.
- Pregnancy, see [Section 6.5.5](#) and [Section 7.6](#).
- Use of prohibited treatment, see [Section 5.5.8](#).
- Any situation in which study participation might result in a safety risk to the subject.
- Emergence of the following AE: ketoacidosis (see also [Section 7.8.1](#)) or lower limb amputation (including toe amputation).
- Any laboratory abnormalities that in the judgment of the investigator, taking into consideration the subject's overall status, prevents the subject from continuing participation in the study.
- Subjects whose study treatment has been unmasked (see [Section 5.5.9](#)).
- Withdrawal of consent (see [Section 5.6.3](#)).

If discontinuation of study treatment occurs, the subject should *not* be considered withdrawn from the study. The subject should return to the study site as soon as possible after

discontinuation of study drug for a study treatment discontinuation visit (see [Table 6-1](#)). TD visit assessments detailed in [Table 6-1](#) should be completed and recorded in the eCRF. The investigator must determine the primary reason for the subject's premature discontinuation of study treatment and record this information on the appropriate eCRF.

After study treatment discontinuation, at a minimum, in abbreviated visits, the following data should to be collected at study site visits or via telephone contact:

- New and/or concomitant treatments.
- AEs/Serious AEs (SAEs).

If the subject cannot or is unwilling to attend any visit(s), the site staff should maintain regular telephone contact with the subject, or with a person pre-designated by the subject. This telephone contact should preferably be done according to the study visit schedule ([Table 6-1](#)).

The investigator must also contact the IRT system to register the subject's discontinuation from study treatment. If study drug discontinuation occurs because treatment code has been broken, please refer to [Section 5.5.9](#).

### **5.6.3 Withdrawal of informed consent**

Subjects may voluntarily withdraw consent to participate in the study for any reason at any time. Withdrawal of consent from the study is defined as when *all* of the following apply:

- A subject does not want to participate in the study anymore *and*
- Does not want any further visits or assessments *and*
- Does not want any further study related contacts *and*
- Does not allow analysis of already obtained biologic material.

In this situation, the investigator must make every effort (eg telephone, e-mail, letter) to determine the primary reason for the subject's decision to withdraw their consent and record this information.

Study treatment must be discontinued (see [Section 5.6.2](#)) and no further assessments conducted, and the data that would have been collected at subsequent visits will be considered missing. Further attempts to contact the subject in the context of the study are not allowed unless safety findings require communicating or follow-up.

All efforts should be made to complete the assessments prior to study withdrawal. A final evaluation at the time of the subject's study withdrawal should be made as per [Table 6-1](#).

### **5.6.4 Loss to follow-up**

For subjects whose status is unclear because they fail to appear for study visits without stating an intention to discontinue or withdraw, the investigator should show "due diligence" by documenting in the eSource system (where applicable) or the source documents steps taken to contact the subject, eg dates of telephone calls, registered letters, etc. A subject cannot be considered as loss to follow-up until the time point of their scheduled end of study visit has passed.

### **5.6.5 Early study termination by the sponsor**

The study can be terminated by Novartis at any time for any reason. This may include reasons related to the benefit risk assessment of participating in the study, practical reasons, or for regulatory or medical reasons (including slow enrolment). Should this be necessary, the subject must be seen as soon as possible and treated as a prematurely withdrawn subject (see [Section 5.6.2](#)). The investigator may be informed of additional procedures to be followed in order to ensure that adequate consideration is given to the protection of the subject's interests. The investigator will be responsible for informing the institutional review board (IRB)/independent ethics committee (IEC) of the early termination of the study.

